The film shows a dialog between a physician and a patient with MSKP. The film is seven minutes long and divided into three sections. Section one (4 minutes 30 secs) presents the idea that MSKP is a complex and necessary biopsychosocial protective system that does not accurately reflect the anatomical state of the body (Moseley & Butler, 2017). Section one also provides reassurance that MSKP is very rarely caused by serious pathology (Finucane et al. 2020). Section two (1 minute 30 secs) provides advice on active coping strategies, such as encouraging exercise and work despite some pain, in an attempt to reconceptualise the commonly held belief that a painful body part needs to be rested (Caneiro et al., 2020; Setchell et al., 2017). Section three (50 secs) aims to prepare patients for their initial physiotherapy consultation by encouraging them to reflect on the time when their MSKP first developed and their overall life situation with the aim of facilitating a more biopsychosocial consultation. Following the film the patients will rate eight statements that summarise the film's key-messages as listed in Table 2.

The film aims to target patients' impeding MSKP illness perceptions, improve pain self-efficacy and encourage adaptive self-management strategies, all factors that are hypothesised to improve pain intensity over time. This requires the content of the film to improve factors such as maladaptive perceptions of the causes of MSKP and its persistence (for example, low outcome expectation, anxiety, catastrophizing, and fear avoidance beliefs) and low pain self-efficacy. The content of the film addresses all the dimensions of the CSM and this is outlined in Table 2 (Leventhal et al., 2016).

Stage two: The consulting physiotherapist will, via four structured questions, initiate a discussion about the film's contents and the questionnaires the patient has completed prior to the initial consultation. The four questions ask the patient if any of the content within the questionnaires they have completed have generated any thoughts or reflections, whether they had actually seen the film, whether the film generated any thoughts or reflections and if there was anything in particular they took from the film. It is hoped that these questions, in addition to the film providing a shared basis for patient-centred MSKP communication, will facilitate a higher value initial consultation (Epstein et al., 2005; Lehman, 2017).

Who

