Patients receive seven questions and physiotherapists 3 questions regarding their experience of the initial physiotherapy consultation. Between group mean difference for responses to these questions will be analysed using independent sample t-tests. These analyses will be presented as mean and SD for each group and the between group difference in mean and CI. Three of the patient questions will be analysed for concordance with the matched physiotherapists' questions. Concordance within the intervention group and control group will primarily be analyzed by calculating intraclass correlation coefficient (ICC) with 95% confidence interval on each question as well as all three questions combined. Two-way random effects model will be used for ICC, assuming raters to be randomly selected. The ratings are single measures analyzed for consistency, to measure systematic differences between ratings. Patients and physiotherapists are treated as two independent raters, rating each of the three questions.

Sensitivity analyses

The following are all re-analyses of the primary and secondary outcomes under different conditions:

- Per-protocol analysis
- Complier average causal effect (CACE) analysis
- Responder analysis
- Complete case analysis (in case of >5% missing data)

Per-protocol analysis

Per-protocol analyses for the primary and secondary outcomes will be conducted to assess robustness of the ITT analyses and to further inform decisions regarding superiority. The sample of the patients for the per-protocol analyses will be as follows:

- Intervention group: patients receiving the PainSMART-strategy with no or minor deviation from protocol.
- Control group: patients receiving intervention with no or minor deviation from protocol.

Data on the physiotherapists' self-reported adherence to the protocol will be cross-referenced with the intervention respective control group patient consultations that each physiotherapist has conducted. This, in combination with the intervention group patients' self-reported exposure to the film, will provide data on deviation from protocol.

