- Intervention group:
 - Responders: patients attaining within group mean change equal to and above the study specific threshold for MCID.
 - Non-responders: patients attaining within group mean change below the study specific threshold for MCID.
- Control group:
 - Responders: patients attaining within group mean change equal to and above the study specific threshold for MCID.
 - Non-responders : patients attaining within group mean change below the study specific threshold for MCID.

The group comparison refers to the difference in responder rates between the intervention and the control group using Chi-square test for independence.

Mediation analysis

The planned mediation analysis of the PainSMART-study will help analyse the causal mechanisms of the PainSMART-strategy. If the PainSMART-strategy is found to be effective, the causal mediation analysis will help explain how the strategy works. Conversely, if the strategy is not found to be effective, the causal mediation analysis will help identify where the hypothesised mechanisms broke down.

Primary mediation objective

The primary objective is to confirm if improvement in hypothesised mediators, MSKP illness perceptions and reassurance of the benign nature of MSKP, mediate the effect of the PainSMART-strategy on pain intensity and pain self-efficacy.

Rationale for the hypothesised mediators

MSKP illness perceptions and level of reassurance as to the benign nature of MSKP are hypothesized, based on an integration of the CSM and concept of self-efficacy, to be potential mediators of the effect of the PainSMART-strategy on pain intensity as well as other secondary outcomes. The integrated model also hypothesizes pain self-efficacy to be a mediator in a series of mediators of the PainSMART-strategy's effects. The theoretical rationale underlying the hypothesised mediators in the PainSMART-strategy are explained in full in the trial protocol.

Outcomes

Primary outcomes are average pain intensity in the previous 24 hours measured with a 11-point NRS and pain self-efficacy measured with PSEQ-10. Hypothesised mediators are MSKP illness perceptions measured with the BIPQ and level of reassurance as to the benign nature of MSKP measured with a 11-point NRS.

Data collection

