To ensure a temporal sequence between the treatment, mediator, and outcome, data was collected over four sequential time points: 1) baseline, prior to randomisation (primary outcome, mediators, confounders); 2) prior to the initial physiotherapy consultation (mediators); 3) 24 hour post initial consultation (mediators); and 4) three months post baseline (primary outcome).

Mediation models and causal model assumptions

Each of the hypothesised mediator's potential effect on each primary outcome will be tested in single mediator models. The potential mediating effect of change in the hypothesized mediators at time point 2 (after exposure to the film) and at time point 3 (after exposure to the whole PainSMART-strategy) will be analysed. An overview of the confirmatory mediator models is presented in Table 1. We assume there to be no confounding of the intervention–mediator and intervention–outcome relationships due to random allocation of the intervention (intervention or control group) (Valeri & VanderWeele, 2013). We assume there to be no confounding of the mediator-outcome relationship following adjustment for the sufficient set of potential observed confounders.

Table 1. Overview of confirmatory mediator models

Model	Mediator Pre physiotherapy consultation	Mediator Post physiotherapy consultation	Outcome 3 months post baseline
1	Illness perceptions	-	Pain intensity
2	Reassurance of benign nature of MSKP	-	Pain intensity
3	-	Illness perceptions	Pain intensity
4	-	Reassurance of benign nature of MSKP	Pain intensity
5	Illness perceptions	-	Pain self-efficacy
6	Reassurance of benign nature of MSKP	-	Pain self-efficacy
7	-	Illness perceptions	Pain self-efficacy
8	-	Reassurance of benign nature of MSKP	Pain self-efficacy

Confounding

Identified potential confounders of the mediator–outcome relationship will be adjusted for in the single mediation analyses. Potential confounders were identified using the disjunctive cause criterion, which involves selection of measured pre-intervention covariates that are hypothesised to be a cause of the mediator, outcome, or both (VanderWeele, 2019). The

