minimum sufficient adjustment set includes age, sex, BMI, pain duration, number of pain sites, comorbidity, employment, level of education, days to initial physiotherapy consultation, analgesic medication consumption and previous health care interventions. The analyses will also be adjusted for physiotherapist characteristics: age, sex, clinical experience and educational level. Baseline measures of the mediator and outcome will also be included in the models.

Statistical analysis

Single causal mediation analysis will be used to analyse the PainSMART's indirect effects on pain intensity (NRS) and pain self-efficacy (PSEQ-10) through improvement in MSKP illness perceptions (BIPQ) and reassurance of the benign nature of MSKP (NRS). The direct acyclic graph model in Figure 2 summarizes these causal inferences.

For each mediator on each outcome the following will be estimated:

1. The effect for the intervention–mediator relationship, the intervention-outcome relationship and the mediator-outcome relationship.
2. The indirect and direct effects of the intervention on the outcome considering the mediator (single mediated effect).
3. The proportion mediated which is the fraction of the intervention-outcome relationship that is explained by the indirect effect.

Regression-based inference approach will be used for causal mediation analysis. The analysis allows the total effect to be broken down into separate effects (paths) using regression coefficients. The mediation models will be estimated using path-analyses within the framework of Structural Equation Modelling, where all the variables are manifest (i.e., measurable). The mediator models will be constructed with the treatment allocation (binary coded variable 0 = control group, 1 = intervention group) as the independent variable. For each mediator model the intervention-mediator effect (a-path), the mediator-outcome effect (b-path), the average causal mediation effect (indirect effect, ab-product), the average direct effect (c'), and the average total effect (c) will be estimated. The indirect effect is the average intervention effect through the mediator; the direct effect is the average intervention effect that works through all other mechanisms, excluding the selected mediator; and the total effect is the average effect of the intervention on the outcome (MacKinnon, 2012). Effects will be reported with 95% CI.

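### The confirmatory mediation analysis rests on no unmeasured mediator-outcome confounding, which no planned analysis probes, and its adjustment set omits the baseline ÖMPSQ

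*SAP*

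**What the plan says.** Both documents list Hypothesis 2 among the confirmatory research questions. SAP, Mediation analysis, Primary mediation objective: "The primary objective is to confirm if improvement in hypothesised mediators" (illness perceptions and reassurance) mediate the effect on pain intensity and pain self-efficacy. SAP, Mediation models and causal model assumptions: "Each of the hypothesised mediator's potential effect on each primary outcome will be tested in single mediator models". Table 1 there lists eight confirmatory models: two mediators, each at time point 2 or 3, and two outcomes at three months.

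The identifying assumption is in the same section: "We assume there to be no confounding of the mediator-outcome relationship following adjustment for the sufficient set of potential observed confounders". Under Confounding, the "minimum sufficient adjustment set includes age, sex, BMI, pain duration, number of pain sites, comorbidity, employment, level of education", days to the first consultation, analgesic consumption and previous healthcare interventions. Also: "The analyses will also be adjusted for physiotherapist characteristics: age, sex, clinical experience and educational level", and "Baseline measures of the mediator and outcome will also be included in the models". The ÖMPSQ is not listed, although SAP, Primary outcome analysis, names its risk category as a candidate covariate. Protocol, Screening tool, says that it is collected at baseline and that distress and fear-avoidance beliefs are among its constructs.

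SAP, Sensitivity analyses, opens: "The following are all re-analyses of the primary and secondary outcomes under different conditions". It lists per-protocol, CACE, responder and complete-case analyses. For mediation, the only further check is the treatment-by-mediator interaction. AGReMA is named for reporting only.

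**The concern.** Randomisation protects the path from the film to the mediator (a). It does not protect the path from mediator to outcome (b), because patients are not randomised to their level of illness perception or reassurance. Both mediators and both outcomes are ratings by the same patient, so anything that moves both after baseline enters the b-path and is reported as part of the indirect effect.

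One plausible route is early recovery. A patient already improving by time point 2 may feel less threatened then and have less pain at three months, without the change in belief having caused the relief. Pain is rated at time points 2 and 3 but is not in the adjustment set. It cannot simply be added, because the film may affect it too.

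The planned 95% intervals reflect sampling error only. A positive result could therefore show that the film changed a questionnaire score, and be read as showing that this change relieved pain or raised self-efficacy. The between-group efficacy estimates are not affected.

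**Working it through.** **Inputs from the documents.** The mediation section gives no power, sample size or confounding figure of its own. Protocol, Sample size, gives 102 per group × 2 groups × 2 subgroups = 408, a doubling to allow mediation and subgroup analyses and not a mediation calculation. With 450 at baseline and about 90% response, 450 × 0.90 = 405, so N = 408 is a fair working figure. (From the stated difference of 2, SD 4, one-sided 0.05 and 80% power, the t-test needs 51 per arm, 102 in total. That is a separate matter.) Adjustment terms, counted one each: 11 patient factors + 4 physiotherapist factors + 2 baseline scores = 17.

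**Inputs that are assumptions.** The residual mediator-outcome correlation ρ after all adjustment (0 to 0.20), and the film's effect on the mediator d (0.2, 0.3 and 0.5 SD).

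**Step 1: smallest correlation that makes the b-path significant.** Residual df = 408 − 3 − 17 = 388 and t = 1.966. r = t/√(df + t²) = 1.966/√(388 + 3.87) = 0.099. Without covariates it is 0.097. At N = 450 it is 0.093–0.095, and at N = 367 (408 less 10%) 0.103–0.105.

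**Step 2: chance that b is significant when its true value is 0.** By Fisher's z, P(b) ≈ Φ(atanh(ρ)·√(N − 4) − 1.96) plus the small opposite tail. For ρ = 0.10: 0.1003 × 20.10 = 2.017, and Φ(0.057) = 0.52.

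**Step 3: chance that a is significant.** With 204 per arm, P(a) ≈ Φ(d·√102 − 1.96), which is 0.52, 0.86 and 1.00 for d = 0.2, 0.3 and 0.5.

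**Step 4: false mediation per model.** The estimates of a and b are independent in the linear model, so the joint-significance rate is P(a) × P(b). The last row is the range over the same values of d when the indirect effect is tested by a simulated Monte Carlo product interval.

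| | ρ = 0 | 0.05 | 0.10 | 0.15 | 0.20 |
|---|---|---|---|---|---|
| P(b) | 5% | 17% | 52% | 86% | 98% |
| d = 0.2, joint | 3% | 9% | 27% | 45% | 52% |
| d = 0.3, joint | 4% | 15% | 45% | 74% | 84% |
| d = 0.5, joint | 5% | 17% | 52% | 86% | 98% |
| Product interval, d = 0.2–0.5 | 2–6% | 8–18% | 22–50% | 41–85% | 49–97% |

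The SAP does not say how the interval for the indirect effect is formed. A Sobel interval gives lower rates: at ρ = 0.10, 8%, 22% and 40% for d = 0.2, 0.3 and 0.5. If d = 0 there is no indirect effect to inflate.

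**Step 5: what a sensitivity analysis would show.** In a linear single-mediator model the indirect effect is zero when the assumed ρ equals the observed adjusted mediator-outcome correlation. By Step 1, a b-path that is only just significant disappears at ρ of about 0.10.

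**The case against.** - **The SAP states its assumption openly and already takes precautions.** Every model adjusts for the baseline mediator and outcome, both mediator times precede the three-month outcome, and covariates were chosen by a named criterion. This has force. Assume a stable trait loading 0.5 on all four scores. Baseline adjustment then leaves a residual correlation of 0.13 down to 0.05, depending on the autocorrelation assumed; at loading 0.4 it leaves 0.09 to 0.03. So a ρ of 0.10 is not trivially small, and 0.15 to 0.20 needs a stronger or time-varying shared cause. The early-recovery route is time-varying. If the mediator's residual correlation with concurrent pain were 0.25, that pain would need a correlation of 0.10/0.25 = 0.40 with pain at three months to give ρ = 0.10.
- **The assumption cannot be tested, and 0.10 is simply the significance threshold at this N.** Both are true. The gap is that no analysis shows how far the result depends on the assumption.
- **A reader might infer that any shared cause makes the indirect effect significant once the film moves the mediator.** The figures do not support this: 8–18% at ρ = 0.05, and at most about an even chance at 0.10.
- **A reader might infer that distress and fear-avoidance were not measured.** The ÖMPSQ covers both and is left out of the set. The BIPQ also has emotional items, and its baseline score enters the models in which it is the mediator.
- **A reader might take the Protocol to name anxiety and catastrophizing as confounders.** It lists "low outcome expectation, anxiety, catastrophizing, and fear avoidance beliefs" as examples of what the film should improve, so they are partly the mediator construct itself.
- **A reader might regard all ratings as unblinded.** Protocol, Blinding, keeps controls unaware that the film exists.

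**Conclusion.** The concern holds in this form. Hypothesis 2 is presented as confirmatory, its identifying assumption is secured neither by randomisation nor by the adjustment set, and neither document plans an analysis that varies it. Leaving out the ÖMPSQ is an avoidable weakness. At N = 408, a residual correlation of about 0.10 is enough for the b-path to reach two-sided significance. It raises the false-mediation rate per model from about 2–6% to about 22–50%, for film effects of 0.2 to 0.5 SD and a product interval.

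These rates rest on assumed ρ and d, a linear model and no true mediator effect. They show how sensitive the conclusion is. They do not show that confounding of this size is present, or that a mediated finding would be false. The consequence is confined to what can be concluded about mechanism. The change is worth making because it is cheap and decides how Hypothesis 2 can be worded.

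**What to change.** 1. Add the baseline ÖMPSQ to the adjustment set in SAP, Confounding, and in Protocol, Mediation analyses.
2. For each of the eight models in Table 1, re-fit the planned path model with the residual mediator-outcome correlation fixed over a range of both signs, for example −0.3 to 0.3. Both signs are needed because the scales run in different directions: a higher BIPQ score is worse, while a higher reassurance or PSEQ-10 score is better. Report the value at which the indirect effect is zero and the value at which its 95% CI first includes zero. State how that interval is computed.
3. In Primary mediation objective, replace the aim of confirming mediation with a claim conditional on no unmeasured mediator-outcome confounding, always reported with those two values. This is a reporting rule. It needs no pass/fail cut-off, for which the documents give no basis.

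Cost: SAP and Protocol wording, and repeated fits of each model with one fixed parameter. No new data are needed. The downside is a little more analysis and a mediation claim that reads less strongly.
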